For the sham group the Alpha-Stim® will not emit electricity. All other procedures will be the same for both the sham group and the active CES group. The current intensity will be preset and locked by the manufacturer. The sham devices will appear identical to the active device.

Intervention: Device: Alpha-Stim

Primary Outcome Measures:

Change in the modifiable suicide risk factors (MSRF's)

To assess the efficacy of adjunctive cranial electric stimulation (CES), specifically Alpha-Stim®, to reduce suicide risk in psychiatric inpatients through a randomized, double-blind, sham-controlled, clinical trial. The primary efficacy outcome measure will be change in the modifiable suicide risk factors (MSRF's) as indicated by a summed global score from rating scales measuring the MSRFs that include depression (Montgomery-Åsberg Depression Rating Scale), anxiety (Hamilton Anxiety Rating Scale), insomnia (The Pittsburgh Sleep Quality Index) and agitation (Agitated Behavior Scale).

Assess adverse effects and safety

To assess safety of adjunctive cranial electric stimulation (CES), specifically Alpha-Stim®, to reduce suicide risk in psychiatric inpatients through a randomized, double-blind, sham-controlled, clinical trial. The primary safety outcome measure will be responses to an adverse effect assessment questionnaire (GASE questionnaire).

Secondary Outcome Measures:

Assess length of stay

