Random forest model predicting Pittsburg Sleep Quality Index score change between the final observation and baseline (PSQI\_Delta).

% variation explained: 13.01%

[figure not shown]
- Meaning that ~87% of the variation is unexplained

Here is the plot showing how the model is converging. Better.

Here are the experimental variables that are explaining the most variation or are the most predictive of the PSQI\_Delta score. It is encouraging that MADRA\_Delta score is one of the best predictors of PSQI\_Delta score.

rf

[figure not shown]
Random forest model predicting Length of Stay (LOS).

% variation explained: 18.7%

- Meaning that ~81% of the variation is unexplained

[figure not shown]
Here is the plot showing how the model is converging.

[figure not shown]
Here are the experimental variables that are explaining the most variation or are the most predictive of the LOS.

rf

[figure not shown]

[figure not shown]
[figure not shown]
I made some box plots of the target variables with notches. If the notches are overlapping that means that the difference is not significant.

MADRA\_Delta

HAMAT\_Delta

I also ran some linear models on the target variables to see if there was a significant proportion of the variation explained by the treatment. Here are the various models. A summary of the results is that none of the target variables explained a significant proportion of the variance in the treatment variable. In addition the treatment variable did not explain a significant proportion of the variance in any of the target variables.

Active vs Sham

```
Call:
lm(formula = dat$Active_vs._Sham ~ dat$MADRA_Delta + dat$PSQI_Delta +
    dat$LOS + dat$HAMAT_Delta)

Residuals:
    Min       1Q   Median       3Q      Max
-0.7116 -0.4783  0.1233  0.4296  0.6952

Coefficients:
                Estimate Std. Error t value Pr(>|t|)
(Intercept)    1.680905   0.272114   6.177 1.85e-06 ***
dat$MADRA_Delta -0.008970   0.014086  -0.637   0.530
dat$PSQI_Delta  0.024970   0.021857   1.142   0.264
dat$LOS        -0.014567   0.011225  -1.298   0.206
dat$HAMAT_Delta 0.006887   0.019592   0.352   0.728
---
Signif. codes:  0 '***' 0.001 '**' 0.01 '*' 0.05 '.' 0.1 ' ' 1

Residual standard error: 0.5104 on 25 degrees of freedom
Multiple R-squared:  0.1317,    Adjusted R-squared:  -0.007216
F-statistic: 0.9481 on 4 and 25 DF,  p-value: 0.4529
```

MADRA\_Delta

```

Call:
lm(formula = dat$MADRA_Delta ~ dat$HAMAT_Delta + dat$PSQI_Delta +
    dat$Active_vs._Sham + dat$LOS)

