Residuals:
    Min       1Q   Median       3Q      Max
-19.1440  -4.4362   0.3207   4.8098  13.4379

Coefficients:
                Estimate Std. Error t value Pr(>|t|)
(Intercept)    -4.75714    4.17875  -1.138  0.265741
dat$HAMAT_Delta  0.84571    0.21889   3.864  0.000703 ***
dat$PSQI_Delta  0.65285    0.28752   2.271  0.032044 *
dat$Active_vs._Sham1 -1.77929    2.79430  -0.637  0.530071
dat$LOS         -0.07574    0.16263  -0.466  0.645431
---
Signif. codes:  0 '***' 0.001 '**' 0.01 '*' 0.05 '.' 0.1 ' ' 1

Residual standard error: 7.188 on 25 degrees of freedom
Multiple R-squared:  0.5498,    Adjusted R-squared:  0.4778
F-statistic: 7.633 on 4 and 25 DF,  p-value: 0.0003661

```

HAMAT\_Delta

```

Call:
lm(formula = dat$HAMAT_Delta ~ dat$MADRA_Delta + dat$PSQI_Delta +
    dat$Active_vs._Sham + dat$LOS)

Residuals:
    Min       1Q   Median       3Q      Max
-10.2459  -2.5605   0.1305   1.8374  11.9851

Coefficients:
              Estimate Std. Error t value Pr(>|t|)
(Intercept)   -5.84565    2.86952  -2.037 0.052353 .
dat$MADRA_Delta  0.44207    0.11442   3.864 0.000703 ***
dat$PSQI_Delta  -0.05453    0.22805  -0.239 0.812978
dat$Active_vs._Sham1 0.71411    2.03158   0.352 0.728154
dat$LOS         0.26534    0.10549   2.515 0.018688 *
---
Signif. codes:  0 '***' 0.001 '**' 0.01 '*' 0.05 '.' 0.1 ' ' 1

Residual standard error: 5.197 on 25 degrees of freedom
Multiple R-squared:  0.5646,    Adjusted R-squared:  0.4949
F-statistic: 8.104 on 4 and 25 DF, p-value: 0.000247

```

PSQI\_Delta

```

Call:
lm(formula = dat$PSQI_Delta ~ dat$MADRA_Delta + dat$HAMAT_Delta +
    dat$Active_vs._Sham + dat$LOS)

Residuals:
    Min       1Q   Median       3Q      Max
-11.3494  -2.1282   0.1626   1.9709   9.8305

Coefficients:
              Estimate Std. Error t value Pr(>|t|)
(Intercept)    0.65390    2.71122    0.241  0.811
dat$MADRA_Delta  0.26188    0.11534    2.271  0.032 *
dat$HAMAT_Delta -0.04184    0.17500   -0.239  0.813
dat$Active_vs._Sham1 1.98695    1.73926    1.142  0.264
dat$LOS        -0.04182    0.10311   -0.406  0.688
---
Signif. codes:  0 '***' 0.001 '**' 0.01 '*' 0.05 '.' 0.1 ' ' 1

Residual standard error: 4.553 on 25 degrees of freedom
Multiple R-squared:  0.2684,    Adjusted R-squared:  0.1513
F-statistic: 2.293 on 4 and 25 DF,  p-value: 0.08759

```

LOS

```

Call:
lm(formula = dat$LOS ~ dat$MADRA_Delta + dat$PSQI_Delta + dat$Active_vs._Sham +
    dat$HAMAT_Delta)

Residuals:
    Min       1Q   Median       3Q      Max

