-12.844  -4.353  -2.341   2.845  23.249

Coefficients:
              Estimate Std. Error t value Pr(>|t|)
(Intercept)    20.0404    3.3876   5.916 3.57e-06 ***
dat$MADRA_Delta  -0.1136    0.2438   -0.466  0.6454
dat$PSQI_Delta  -0.1563    0.3854   -0.406  0.6885
dat$Active_vs._Sham1 -4.3329    3.3387   -1.298  0.2062
dat$HAMAT_Delta  0.7611    0.3026    2.515  0.0187 *
---
Signif. codes:  0 '***' 0.001 '**' 0.01 '*' 0.05 '.' 0.1 ' ' 1

Residual standard error: 8.802 on 25 degrees of freedom
Multiple R-squared:  0.3168,    Adjusted R-squared:  0.2075
F-statistic: 2.898 on 4 and 25 DF,  p-value: 0.04239

```

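### Length of stay is fitted untransformed by least squares although its residuals are right-skewed, and no skew-tolerant or sensitivity analysis is shown; precision may be lost, but validity is not.

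*SAP*

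**What the plan says.** The protocol's secondary outcome entry reads "Assess length of stay" and names no scale or estimand. The SAP's LOS linear model is "lm(formula = dat$LOS ~ dat$MADRA_Delta + dat$PSQI_Delta + dat$Active_vs._Sham" plus the Hamilton change score, with LOS in days and no transformation. The printed residual summary (minimum, quartiles, median and maximum; the first value is negative) is "12.844 -4.353 -2.341 2.845 23.249". The arm row is "dat$Active_vs._Sham1 -4.3329 3.3387 -1.298 0.2062" and the fit lines are "Residual standard error: 8.802 on 25 degrees of freedom", "Multiple R-squared: 0.3168, Adjusted R-squared: 0.2075" and "F-statistic: 2.898 on 4 and 25 DF, p-value: 0.04239". The text before the models concludes that treatment explained no significant share of the variance in any target variable. LOS was also put through a random forest ("variation explained: 18.7" per cent), which gives no estimate or interval for the arm difference.

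**The concern.** Stays cannot be negative and often have a long upper tail. Least squares on raw days then lets the tail set the error variance, and with it the width of the interval for the arm difference. This matters more for LOS than for the other outcomes. It is the listed secondary outcome, and it has the largest unadjusted standardised arm difference of the four modelled: LOS -0.58, PSQI 0.39, Hamilton -0.20, Montgomery-Åsberg -0.13. The same model also conditions on three outcomes measured after randomisation, so its arm coefficient is not the total effect on LOS. Changing the error model alone would not cure that.

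**Working it through.** **1. The printed output reproduces.** t = -4.3329/3.3387 = -1.298, p = 0.2062 on 25 df. F = (0.3168/4)/(0.6832/25) = 2.898. Adjusted R² = 1 - 0.6832 × 29/25 = 0.2075.

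**2. Residual shape, LOS model.**
- Quartile skewness = (Q1 + Q3 - 2 × median)/(Q3 - Q1) = (-4.353 + 2.845 + 4.682)/7.198 = 0.44.
- Maximum/|minimum| = 23.249/12.844 = 1.81.
- Upper Tukey fence = 2.845 + 1.5 × 7.198 = 13.6, and the maximum is beyond it. Lower fence = -4.353 - 10.797 = -15.2, and the minimum is inside it.
- Residual sum of squares = 25 × 8.802² = 1936.9. The largest residual contributes 23.249² = 540.5, or 27.9%.

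The same quantities for all four outcome models:

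| Model | Quartile skewness | Max/\|min\| | Residual SE ÷ (IQR/1.349) |
|---|---|---|---|
| LOS | 0.44 | 1.81 | 1.65 |
| Montgomery-Åsberg change | -0.03 | 0.70 | 1.05 |
| Hamilton change | -0.22 | 1.17 | 1.59 |
| PSQI change | -0.12 | 0.87 | 1.50 |

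In 100,000 simulated normal-error fits with 30 patients and 5 coefficients, quartile skewness of at least 0.44 has probability 0.028, max/|min| of at least 1.81 has 0.020, and a spread ratio of at least 1.65 has about 0.025.

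**3. Arm means and SD, rebuilt from the five printed models.** The five models regress each of the same five variables on the other four. The inverse of the corrected sums-of-squares matrix therefore has diagonal entries 1/(25 × RSE²) and off-diagonal entries -b/(25 × RSE²). Inverting it gives:
- Treatment sum of squares 7.50 = 15 × 15/30, so 15 per arm.
- LOS total sum of squares 2834.9. Check from R²: 1936.9/0.6832 = 2835.0.
- Unadjusted arm difference -5.60 days.
- Within-arm SD = √[(2834.9 - 7.5 × 5.60²)/28] = 9.64.

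Solving the four outcome intercepts, with the arm indicator averaging 0.5, gives a mean LOS of 13.4 (402 days in total). The arm means are 13.4 ± 2.8, that is 16.2 and 10.6 days, with arm totals of 243 and 159. All four outcome totals come out as whole numbers to rounding (402, -476, -264, -81), which supports the rebuild. The output does not say which arm is coded 1.

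Unadjusted SE = 9.64 × √(2/15) = 3.52, so t = -1.59, p = 0.12, 95% CI -12.8 to 1.6 days. A normal model for the shorter-stay arm puts Φ(-10.6/9.64) = Φ(-1.10) = 13.6% of stays below zero.

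**4. Power, raw against log.** Settings: 40,000 simulated trials per row, 15 per arm, the means above, pooled SD 9.64, two-sided 5% t-test, and the same coefficient of variation in both arms above an assumed minimum stay.

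| Shape | Minimum stay (days) | Raw | Log | Change (points) |
|---|---|---|---|---|
| Log-normal | 0 | 36% | 42% | +6 |
| Log-normal | 2 | 37% | 45% | +8 |
| Log-normal | 4 | 39% | 49% | +10 |
| Gamma | 0 | 33% | 30% | -3 |
| Gamma | 2 | 33% | 31% | -2 |
| Gamma | 4 | 32% | 33% | +1 |

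With equal means, the raw test rejects in about 4 to 5% of trials.

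**5. Could the conclusion turn on this?** With the printed coefficient held at -4.33, p = 0.05 needs an SE of 4.3329/2.0595 = 2.104. That is a residual SE of 2.104/3.3387 × 8.802 = 5.55, 37% below the printed 8.80. Removing the largest residual (leverage assumed 0.05 to 0.40) takes it only to about 7.5 to 6.6. In the unadjusted comparison, log-normal stays would give an expected log-scale t of about 1.8 (p about 0.08), against 1.6 raw.

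**The case against.** The strongest reply is that nothing here is invalid. Least squares is unbiased for a difference in mean days whatever the skew, the raw test holds its size, and the printed conclusion probably survives. All of that stands.

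A reader might also infer that a few long stays demonstrably inflate the error term and cost precision. The documents do not support that, for four reasons.
- The printed quantiles prove one extreme residual. Residual sets that match the printed summary have between 1 and 4 beyond the upper fence, with moment skewness from 0.43 to 1.90. A large residual is also not the same as a long stay, because the model conditions on three change scores.
- A residual SE well above the quartile-based scale is not specific to LOS: the Hamilton and PSQI models show nearly the same ratio without right skew. Nor is the 28% share specific, since the lowest Montgomery-Åsberg residual holds 19.144²/(25 × 7.188²) = 28% of its own sum of squares. What sets LOS apart is the direction of the asymmetry.
- Whether a log analysis gains power depends on the shape of the stays, which the output does not reveal.
- It also depends on how the spread divides between arms. If both arms had SD 9.6 (minimum stay 0), log-scale power would be about 62% (log-normal) or 54% (gamma), partly because the log test then responds to differences in shape as well as in mean.

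Finally, moving to the log scale after seeing the residuals and p-values, in a direction expected to raise the test statistic, is open to criticism. That also stands and shapes the fix.

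**Conclusion.** The point holds as a minor one. The LOS residuals are right-skewed where those of the change-score models are not, a normal model at the recovered means implies about 14% negative stays in one arm, and the supplied text offers no check on the error model. The possible loss is about 6 to 10 points of power if stays are log-normal, and roughly none if they are gamma. It is not a validity error and probably does not overturn the non-significant result. Taking the co-outcomes out of the model moves the estimate from -4.3 to -5.6 days, still with p = 0.12.

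The 15-per-arm split, the means and the SD follow from the printed output. The power figures rest on assumed shapes, minimum stays of 0 to 4 days and a common coefficient of variation. The residual shape is after the SAP's covariates, so it only approximates the within-arm shape. Parts of the SAP and its figures are not in the supplied text, so a check made there cannot be excluded.

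**What to change.** Compare LOS by arm alone, with no other outcome in the model. Keep the difference in mean days and give it a bootstrap 95% CI. Beside it, report `log(LOS) ~ arm` as a ratio of geometric mean stays with its 95% CI. Label the log result post hoc, because the residuals and p-values have already been seen, and do not let it replace the difference in days. The log needs every stay to be above zero, which should be confirmed in the data.

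The cost is a few lines of R and a sentence or two in the SAP. The downside is a second scale to explain: a ratio of geometric means is a different quantity from a difference in mean days, and the two need not agree.
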